Subjects will be followed weekly with ratings of PTSD symptoms, mood and anxiety, as well as examinations for risk of suicidality. Week 8 endpoint measures will include severity and frequency of PTSD symptoms, quality of sleep, and quality of life measures. The primary endpoint measure is the change in symptom severity at the week 8 visit. The week 8 time point will be used to compare changes in symptoms between subjects who were randomly assigned to the active vs. sham TNS treatment condition. Subjects also will be interviewed an additional 4 weeks after the conclusion of the sham controlled treatment, and their mood and anxiety symptoms assessed, to examine the durability of any symptom change that subjects experienced during the initial 8 weeks. At the end of week 8, subject improvement will be assessed and those showing a $\geq 25\%$ improvement from baseline at the end of 8 weeks of treatment will be eligible to participate in the 42-month extension phase to monitor and observe possible benefits of prolonged TNS in responders. Subjects who participate in the extension phase will remain blinded. Subjects complete the PCL-M and BDI monthly during their participation in the extension phase. The PCL-M monthly score determines on-going inclusion in this phase. Subjects will be withdrawn in the case of adverse events, or symptom worsening (quantified as > 25%worsening in symptoms after one month as compared to the beginning of the extension phase as assessed using the PCL-M total score). Subjects way also voluntarily withdraw from the extension phase at any time.

Subjects who do not participate in the extension phase will be unblinded and told whether they received the active or sham-controlled treatment after all study and follow-up visits have been completed. This includes completion of the eight-week double-blind treatment phase and four-week follow-up phase for a total of 12 weeks in this study. Data will be examined for differences

between active and sham treatment, as well as safety and acceptability of the treatment. If positive, this preliminary study will serve as the basis for a larger pivotal trial of effectiveness.

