Screening Procedures and Instruments: After signing the consent form, the research coordinator will interview subjects to ask about demographic data and assess for possible exclusion criteria. The instruments listed below will be used to determine eligibility for the study and assess symptom severity. Instruments will be administered on the schedule shown in Table 1 below. Clinician-Administered PTSD Scale for DSM-V (CAPS-5-5) (Blake et al., 1995; Weathers et al., 2001): The CAPS-5 will be used both to establish eligibility for inclusion in the protocol and as an outcome measure. This 30-item structured interview assesses the presence, frequency, and severity of symptoms of PTSD. It provides a continuous score of frequency and severity for each symptom, with overall severity characterized by summing the total score for the individual items. The CAPS-5 has good psychometric properties across a wide variety of clinical populations and research settings (Weathers et al., 2001). We first will determine using the CAPS-5-5 whether the subject has at least one Criterion A stressor related to warzone exposure. If the subject meets this criterion, the remainder of the CAPS-5-5 will be administered to confirm the presence of PTSD and assess severity. Frequency and severity of symptoms are rated separately on a 0-4 scale.

Mini International Neuropsychiatric Interview for DSM-IV, Version 5.0 (MINI) (Sheehan et al.,1998): The MINI is a short yet accurate structured diagnostic interview used to diagnose current and lifetime Axis I disorders according to DSM-IV criteria. The assessment takes approximately 15 minutes to administer (Sheehan et al., 1998) We will specifically assess current substance dependence, current and/or history of psychosis, bipolar disorder, and to assess possible presence of exclusion criteria through use of relevant modules from the MINI. We also will utilize this instrument to determine the presence of Major Depressive Disorder (MDD); subjects will not be ruled-out because of the presence of MDD, but the presence of the illness will be used as a covariate. If presence of MDD appears to affect outcome, we may perform a subgroup analysis in subjects with comorbid MDD.

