Following the baseline assessment, subjects then will be randomized to one of the two treatment conditions. Treatment assignment will be randomized within cells defined by gender, symptom severity, and presence of current medication treatment to provide a degree of balance on key underlying characteristics that otherwise would have the potential to confound the interpretation of study findings. Specifically, there will be eight strata for randomization defined by the 2 x 2 x 2 combinations of gender (male or female), symptom severity (lower or higher defined by whether the CAPS-5 score on entry is less than 78, the median value for this sample, versus being 78 or greater), and presence of current medication treatment (yes or no). Within these strata, randomization will occur in blocks of two, so that after every two patients with a given combination of stratum-defining characteristics, there will be one patient assigned to the active intervention and one to the control arm. The randomization will be carried out by associating strata with rows of the random-number table in Cochran (1977, p. 19). For the first member of each successive pair of patients presenting with a given set of stratum-defining characteristics, if the next number in the row is in the range of 5 through 9, then the patient will be assigned the active intervention, else the patient will be assigned to the sham. If the first subject was assigned the active intervention, then the next subject would be assigned the sham, and vice versa; for the next subject after that, the random-number table will be used in the same way. The pairing in the design could be considered in the analysis, and we will plan to do so using a permutation-test approach for purposes of being complete. The core motivation for the pairing, however, is to ensure that treatment assignment remains balanced across arms rather than because we believe that there is anything scientifically important about whether the subject arrives at an odd or an even number in the sequence. For our primary analysis, we will use a randomized-block ANOVA that accounts for the 2 x 2 x 2 stratification in the design but does not reduce the error degrees of freedom on account of the pairing.

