TNS is a relatively new treatment, so there are limited published data from sham-controlled studies. All data available to date, however, show a pattern of consistent efficacy for TNS in alleviating mood and anxiety symptoms in patients with epilepsy, MDD, and PTSD (Cook et al., 2014). Significant improvements in mood have been described with TNS in an open-label study of subjects with MDD (Schrader et al., 2011; Cook et al., 2013) and a controlled trial of epilepsy (DeGiorgio et al., 2011).

We recently concluded an open-label trial of TNS in adults with PTSD and comorbid MDD. Twelve adults (mean age 52.8 (13.7 s.d.) years, 8F:4M) with median 37 yrs since traumatic exposure (range 3-61) and with PTSD and MDD, were studied in an 8-week open label outpatient trial. Three of these subjects had PTSD based upon military service. Current episodes were required to be of at least 4 months duration, with non-response to at least 1 antidepressant trial over at least 6 weeks during the current episode (ATHF ≥ 1), and concomitant use of at least 1 antidepressant. All had prominent symptoms at entry, with mean scores on the CAPS-5 of 80.2 (12.5), PTSD Patient Check List (PCL) of 63.3 (7.8), of 25.8 (4.6) on the 17-item Hamilton Depression Rating Scale (HDRS), and of 17.8 (4.0) on the Quick Inventory of Depressive Symptomatology (QIDS-C). Subjects placed stimulating electrodes over the supraorbital branches of the trigeminal nerve for at least 8 hours each night, primarily while asleep, with current adjusted to maximal comfortable levels. Co-primary outcomes were change in PCL and QIDS-C at 8 weeks. Results show that TNS was well tolerated, with no subjects discontinuing treatment because of difficulty or unacceptability of using the device. Decreases in PCL score were significant, from 63.3 (7.8) at entry to 43.0 (18.3) at week 8 (2-tail paired t-test p=0.003). QIDS-C score decreases were also significant, falling from 17.8 (4.0) to 8.8 (4.3) (p<0.001), as were scores on the HDRS, improving from 17.8 (4.0) to 11.9 (7.3) p<0.001). All reflect a large effect size comparing end-of-trial to start (Cohen's d 1.5 for PCL, 1.8 for QIDS-C, and 2.1 for HRSD). We do not have data on the durability of these effects.

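### The primary change-score ANOVA is valid but uses baseline severity only by subtraction and a split at 78; adding the continuous baseline score is an optional, cheap efficiency improvement of uncertain size

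*Combined protocol and SAP*

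**What the plan says.** Section 13, Overview, defines the endpoint: "The primary endpoint measure is the change in symptom severity at the week 8 visit". That sentence names no instrument.

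Section 13, Conduct of the study, gives the model: "For our primary analysis, we will use a randomized-block ANOVA that accounts for the 2 x 2 x 2 stratification in the design". It adds that the model "does not reduce the error degrees of freedom on account of the pairing", and plans a permutation test that respects the pairing. The three stratum factors are gender, current medication and severity, the last defined by "whether the CAPS-5 score on entry is less than 78, the median value for this sample, versus being 78 or greater".

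Section 13, Screening Procedures and Instruments, says of the CAPS-5: "It provides a continuous score of frequency and severity for each symptom". It is both an eligibility and an outcome measure, and Table 1 schedules it at weeks 0, 4 and 8. A continuous total therefore exists before randomization.

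Conduct of the study also repeats the CAPS-5 at a second baseline visit, after randomization and just before treatment starts. Nothing says which of the two scores is the baseline for change.

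The only covariates named are presence of MDD (section 13) and, if the arms are unbalanced on it, uncontrolled treatment (section 12). Neither is baseline severity.

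**The concern.** A change score fixes the slope of week 8 on baseline at 1. If the true slope differs, baseline still predicts the change, and the two-level stratum removes only part of that. What remains inside each stratum adds to the error variance, and the blocks do not balance it between arms. A continuous covariate would let the data estimate the slope.

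What is at stake is the precision of the treatment effect with 37 patients per arm. Validity is not at stake: randomization protects the planned comparison, and its simulated type I error is close to 5%.

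**Working it through.** **The plan's own figure.** Only 2 x 37 = 74 can be checked. The documents give no alpha, power, effect size, CAPS-5 correlation or week-8 CAPS-5 SD, so the gain can only be shown over assumed values.

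**Inputs from the documents.** N = 74; eight strata; cut at 78; entry floor 50 (section 12); pilot entry CAPS-5 mean 80.2, SD 12.5 (section 16).

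**Assumed.** CAPS-5 is the scale; change is taken from the entry score; scores are bivariate normal; correlation r is 0.3 to 0.7. Let k be the ratio of week-8 SD to entry SD, and b = r x k the slope.

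**Formula.** Let w be the share of baseline variance left within the two severity levels. For a normal distribution with the pilot mean and SD, truncated at 50 and cut at 78, w = 0.365. Error df are 74 - 8 - 1 = 65, or 64 with the covariate. The variance of the treatment effect under the planned model, relative to the same model plus the continuous score, is

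[1 + w(1 - b)² / (k²(1 - r²))] x 64/65.

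- Equal SDs, r = 0.3: 0.365 x 0.49/0.91 = 0.197; 1.197 x 64/65 = 1.178.
- k = 1.5, r = 0.5 (b = 0.75): 0.365 x 0.0625/1.6875 = 0.0135; 1.0135 x 64/65 = 0.998.

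**Simulation.** 74 patients, stratified blocks of two, 20,000 runs per case. Further assumptions: 10% female, 75% medicated, no dropout, MDD in neither model. Values above 1 favour the covariate.

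| SD ratio k | r = 0.3 | r = 0.5 | r = 0.7 |
|---|---|---|---|
| 1.0, formula | 1.178 | 1.104 | 1.048 |
| 1.0, simulated | 1.169 | 1.099 | 1.045 |
| 1.08, simulated | 1.133 | 1.069 | 1.021 |
| 1.5, simulated | 1.035 | 0.997 | 0.985 |
| 1.59, simulated | 1.025 | 0.993 | 0.988 |

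If the planned model had 80% power, the amended one would have 86, 84 and 82% at equal SDs, and 81, 80 and 79% at k = 1.5. Type I error was 4.8 to 5.2% as planned and 4.6 to 5.2% with the covariate. At equal SDs and r = 0.5, other gender and medication mixes gave 1.097 to 1.098.

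**Pilot as a rough guide** (section 16: 12 open-label subjects, other scales).

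- QIDS-C, "QIDS-C score decreases were also significant, falling from 17.8 (4.0) to 8.8 (4.3"): k = 4.3/4.0 = 1.08.
- HDRS: k = 7.3/4.6 = 1.59, using the entry SD first given; the same section later gives 4.0, which makes it 1.83.
- PCL, "Decreases in PCL score were significant, from 63.3 (7.8) at entry to 43.0 (18.3) at week 8": k = 18.3/7.8 = 2.35. The paired p = 0.003 on 11 df gives t = 3.79, so the SD of change is 20.3 x √12/3.79 = 18.56. Then r = (7.8² + 18.3² - 18.56²)/(2 x 7.8 x 18.3) = 0.18. The formula gives 1.007 and the simulation 1.006. Rounding of p allows r from 0.24 to 0.12, or 0.997 to 1.017.

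**Downside.** The bracketed term is never below 1, so the loss comes only from the extra coefficient: 64/65 = 0.985 at N = 74, and 50/51 = 0.980 with 60 completers.

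**If the two baselines differ.** Suppose planned change is taken from the repeat score, test-retest correlation is 0.9, and week 8 tracks the repeat (r = 0.7) more closely than the entry score (0.9 x 0.7 = 0.63). Compare this with a model of week 8 adjusted for the entry score, in units of the entry variance.

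- Equal SDs. Planned: 2 - 1.4 - 0.635 x (0.63 - 0.9)² = 0.554. Alternative: 1 - 0.63² = 0.603. Ratio 0.554/0.603 x 64/65 = 0.90, a loss of about 10%.
- k = 1.5. Planned: 2.25 + 1 - 2.1 - 0.635 x (0.945 - 0.9)² = 1.149. Alternative: 2.25 x 0.603 = 1.357. Ratio 1.149/1.357 x 64/65 = 0.83, a loss of about 17%.

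Here 0.635 is 1 - w.

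**The case against.** The plan already subtracts baseline and blocks on severity, so only about 36% of the baseline variance remains within the severity levels. Two-level adjustment is a defensible choice, and no statement in the documents is contradicted. All three pilot SD ratios exceed 1, and the only PTSD scale with a follow-up SD gives a gain near zero. All of this stands, and it is why the point is optional. Twelve open-label subjects on other scales cannot rule out a useful gain, but they do not point to one.

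The repeat CAPS-5 is also a fair objection. It is a plausible baseline for change, and adjusting for a different score from the one subtracted or replaced can cost far more than one degree of freedom. That is met only by tying the covariate to the baseline for change.

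MDD is to be a covariate, though the protocol does not say in which analysis; the simulation leaves it out of both models. The planned model may therefore differ somewhat from the one simulated.

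A reader might infer that the split makes the primary test biased or invalid. The documents do not support that: allocation is randomized within the strata that the model contains.

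**Conclusion.** The point holds as a modest efficiency suggestion and ranks below any question of validity. With change taken from the entry score, the gain is about +17, +10 and +4% at r = 0.3, 0.5 and 0.7 with equal SDs, about +3, 0 and -1.5% at SD ratio 1.5, and about +0.6% on the pilot PCL figures. At equal SDs this equates to about 87, 81 and 77 patients under the planned model in place of 74; on the PCL figures it stays at 74.

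A reader might take +17% as the expected gain or as a ceiling. It is neither. It needs equal SDs and r = 0.3, which the documents do not supply, and other inputs give more (about +34% at SD ratio 0.8, r = 0.3). Only the lower end is firm: about -1.5% at N = 74, or -2% with 60 completers, and then only if the covariate and the baseline for change are the same score. The gain vanishes as the slope approaches 1.

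Confidence is medium, because CAPS-5 as the primary scale and the choice of baseline are both inferred.

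**What to change.** State in the primary analysis that the instrument is the CAPS-5, if that is intended, and whether the baseline for change is the entry score that sets the stratum or the repeat taken just before treatment. Keep the 2 x 2 x 2 strata and add that same score as a continuous covariate. The outcome may be week-8 CAPS-5 or change from that score; with the same score as covariate, both give the same treatment effect. Keep the planned blocked ANOVA and the permutation test as sensitivity analyses, and settle the wording before unblinding.

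No new data are needed. One error degree of freedom is lost (65 to 64), which in the worst case moves 80% power to 79%. The choice of instrument and baseline is more than a wording change, but the change-score endpoint needs both settled anyway.

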Inquiry (SAFTEE-SI) (Levine and Schooler, 1986), an easy to use 55-item self-report (with an additional overall severity item) that rates most commonly reported side effects expected with the clinical study interventions. While developed for medication studies, it is applicable to device studies as well, and will be used to describe side effects associated with treatment. The SAFTEE-SI will be administered at enrollment and at each follow-up visit, to detect treatment-emergent events or events which worsen during treatment. The SAFTEE-SI will be supplemented by an open-ended question ("general inquiry") to capture any adverse reactions not enumerated in the SAFTEE-SI items. Events will be categorized using the Medical Dictionary for Regulatory Affairs (MedDRA), a clinically validated terminology that applies to all phases of drug and medical device development, and developed by the International Conference on Harmonisation (ICH) as a successor to the earlier COSTAR ("Coding Symbols for Thesaurus of Adverse Reaction") nomenclature.

Scales from the Deployment Risk and Resilience Inventory-2 (DRRI-2) (baseline)

This 'Trauma and Adversity Exposure' protocol includes the following four self-reported, deployment-related subscales from the Deployment Risk and Resilience Inventory-2 (DRRI-2) (Vogt et al., 2013): Difficult Living and Working Environment (14 items); Combat Experiences (17 items); Aftermath of Battle (13 items); and Perceived Threat (12 items). Items are rated on Likert-style scales and added together to give a score for each scale. See: http://www.ptsd.va.gov/PTSD/professional/assessment/deployment/index.asp

Difficult Living and Working Environment Scale (14 items) DRRI-2 Section: C; Survey Label: "Deployment Environment." This scale assesses exposure to events or circumstances representing repeated or day-to-day irritations and pressures related to life during military deployment. These personal discomforts or deprivations may include the lack of desirable food, lack of privacy, poor living arrangements, uncomfortable climate, cultural difficulties, and constraints to performing one's duties.

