Visit Type	Week 0 (Baseline)	Week 1	Week 2	Week 3	Week 4	Week 5	Week 6	Week 7	Week 8
Visit Length	*6 hrs	2 hrs	2 hrs	2 hrs	4 hrs	2 hrs	2 hrs	2 hrs	4 hrs
Questionnaire /Survey:									
MINI	Х								
CAPS-5	Х				Χ				Х
PTAQ	Х								
PCL-M	Х	Χ	Х	Х	Χ	Χ	Χ	X	Х
BDI	Х	Х	Х	Х	Χ	Χ	Χ	Х	Х
ASI	Х								Х
SF-36	Х				Х				Х
PSQI	Х	Х	Х		Х				Х
SAFTEE-SI	Х	Х	Х	Х	Х	Х	Х	Х	Х
DRRI-2 (4 scales)	Х								
LEC-5	Х			ĺ	Ì				Ì
E-TRIP	Х		ĺ	i i					İ
Treatment Blinding Questionnaire									х
Safety and Compliance		Х	Х	Х	Х	Х	Х	Х	Х
Study Procedures:									
Urine Test	Х								
Pregnancy Test (Females only)	Х								
Simulation Log Check	Х	х	Х	Х	Х	Х	Х	Х	х
Device Setting Adjustments	х				Х				

Table 1 Schedule for administration of diagnostic and rating instruments in the main study

Visit Type	Monthly	Final visit					
Visit Length	30 mins	4 hrs					
Questionnaire/Survey:							
MINI		Х					
CAPS-5		Х					
PTAQ		Х					
PCL-M	X	Х					
BDI	X	Х					
ASI		Х					
SF-36		Х					
PSQI		Х					
SAFTEE-SI		Х					
DRRI-2 (4 scales)		Х					
LEC-5		Х					
E-TRIP		Х					
Treatment Blinding Questionnaire							
Safety and Compliance	Х	Х					

Table 2: Schedule for administration of diagnostic and rating instruments in the extension phase

MINI Version 5.0: Mini International Neuropsychiatric Interview for DSM-IV

CAPS-5: Clinician-Administered PTSD Scale for DSM-V

PTAQ: Post-traumatic Amnesia Questionnaire

PCL-5: PTSD Checklist for DSM-V BDI: Beck Depression Inventory ASI: Addiction Severity Index

SF-36: 36-item Short Form Health Survey

PSOI: Pittsburgh Sleep Quality Index

SAFTEE-SI: Systematic Assessment for Treatment Emergent Events-Systematic Inquiry

LEC-5: Life Events Checklist for DSM-5, self-report

E-TRIP: Emory Treatment Resistance Interview for PTSD

Treatment Blinding Questionnaire: Survey to assess what treatment is thought to be received DRRI-2 Section C, Deployment Environment: 14-item scale assesses exposure to events or circumstances representing repeated or day-to-day irritations and pressures related to life during military deployment.

DRRI-2 Section D, Combat Experiences: 17-item scale assesses exposure to combat-related circumstances.

DRRI-2 Section E, Postbattle Experiences: 13-item scale assesses exposure to the consequences of combat.

DRRI-2 Section G, Deployment Concerns: 12-item assesses fear for one's safety and well-being during deployment.

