Following randomization, subjects will be scheduled to come back for a second visit when they will be given a pre-programmed stimulator, a supply of electrodes, and instructions on how to apply the electrodes and use the device. No more than one week will elapse between the first and second baseline visits. Baseline measures will not be repeated at the second baseline visit except for the CAPS-5, PCL-5, and BDI measures, which will be repeated in order to have PTSD, anxiety, and depression severity measures immediately prior to the start of treatment. Subjects will return to UCLA or the VA GLA for weekly visits and will undergo assessment of symptoms with instruments as specified in Table 1 above. The research coordinator will assess compliance, ensure that the device continues to be in good working order and that the subject has a sufficient supply of electrodes, and encourage continued compliance. In addition, the research coordinator will assess the subject for safety, inquiring specifically about any suicidal ideation and evaluate the results of scheduled assessments. If the research coordinator has any concerns about subject safety, she will immediately contact a study physician who will interview the subject and perform an independent assessment. Subjects will be removed from the study and hospitalized for any safety concerns per the procedure in the Human Subjects section.

At the conclusion of the main study (week 8 visit or sooner if the subject drops out or is removed from the study), subject improvement will be assessed and those showing a \geq 25% improvement from baseline at the end of 8 weeks of treatment will be eligible to participate in the 42-month extension phase to monitor and observe possible benefits of prolonged TNS in responders. Subjects who participate in the extension phase will remain blinded and will be asked to complete the Beck Depression Inventory(BDI) and the PTSD checklist during a monthly phone visit. Subjects who do not participate in the extension phase will be unblinded and told whether they

received the active or sham-controlled treatment after all study and follow-up visits have been completed. The device will be collected from the subject and the subject will be continue treatment in the PTSD Clinic or the Domiciliary Care Program. A summary of the results for each subject in the study will be provided to the clinic staff with the subject's permission.

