Foreseeable risks of participation. It is possible that some subjects may suffer a worsening of symptoms as a result of the assessments or discussing traumatic experiences during the intake process. The assessments are likely to be no more upsetting, however, than standard clinical assessments and treatment. Because subjects will recently have completed a course of PE treatment, they will be familiar with discussions of their symptoms and should not suffer any significant change in their condition.

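### The SAFTEE-SI is not repeated when the device is issued, so symptoms arising in the preceding week may be misclassified as treatment-emergent (minor)

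*Combined protocol and SAP*

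**What the plan says.** - **Checklist timing and purpose** (section 13, Screening Procedures and Instruments): "The SAFTEE-SI will be administered at enrollment and at each follow-up visit, to detect treatment-emergent events or events which worsen during treatment". It is a 55-item self-report with one further item for overall severity. In addition, "The SAFTEE-SI will be supplemented by an open-ended question".
- **Device issue** (section 13, Conduct of the study): after the baseline assessment and randomization, "subjects will be scheduled to come back for a second visit when they will be given a pre-programmed stimulator". On the interval: "No more than one week will elapse between the first and second baseline visits".
- **What is measured at device issue** (same section): "Baseline measures will not be repeated at the second baseline visit except for the CAPS-5, PCL-5, and BDI measures". The reason given for repeating those three is "in order to have PTSD, anxiety, and depression severity measures immediately prior to the start of treatment".
- **Table 1** ("Schedule for administration of diagnostic and rating instruments in the main study"): the SAFTEE-SI is marked in a single Week 0 column and at Weeks 1 to 8. There is no separate column for the second baseline visit.
- **Other adverse-event sources**: a subject log booklet that the coordinator checks weekly (section 13) and physician assessment of reported events (Management of the Risks of Participation).

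Nowhere do the documents define treatment-emergent, name the reference reading for new or worse, or require an onset date.

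**The concern.** An event can be called emergent only relative to a reading taken before exposure, and the closer that reading is to first exposure, the fewer background symptoms are attributed to treatment. Here the efficacy scales are refreshed just before the device is issued, but the scale meant to detect emergent events is not. The Week 1 checklist can be compared only with the enrollment checklist, so the comparison covers the pre-device gap as well as the first treatment week.

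Safety and acceptability are stated questions of the study, and a positive result is meant to support a larger pivotal trial (section 13, Overview). If gap symptoms are tallied as emergent, absolute event rates are raised in both arms. The active-to-sham risk ratio is also pulled toward 1, which makes a real device effect a little harder to see.

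**Working it through.** The plan states no adverse-event rate or counting rule, so there is no figure to reproduce. The timing follows from the text. The size can only be illustrated.

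**Step 1: timing.** Last pre-treatment SAFTEE-SI: enrollment. Device issue: second baseline visit, at most 7 days later. SAFTEE-SI at that visit: no. First later reading: Week 1. The uncovered window is 0 to 7 days.

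**Step 2: share of background onsets that predate the device.** Assume a constant background onset rate and symptoms that persist to the next reading. With a gap of g days, the share is g/(g + 7) at Week 1 and g/(g + 56) over the eight weeks.

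| Gap (days) | Week 1 | Eight weeks |
|---|---|---|
| 1 | 1/8 = 12.5% | 1/57 = 1.8% |
| 3 | 3/10 = 30.0% | 3/59 = 5.1% |
| 5 | 5/12 = 41.7% | 5/61 = 8.2% |
| 7 | 7/14 = 50.0% | 7/63 = 11.1% |

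These shares apply to background symptoms only, not to symptoms that the device causes. The problem is concentrated in the first comparison and is small over the whole period.

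**Step 3: effect on the contrast between arms.** Let p be the true on-treatment incidence and b the gap incidence, the same in both arms, with every gap symptom persisting and being counted. The observed rate is 1 − (1 − p)(1 − b), so the observed risk difference is (1 − b) times the true one. All rates below are assumed.

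A coherent choice of b takes the sham rate as background over 56 days and scales it to 7 days: b = 1 − (1 − p_sham)^(7/56). For p_sham = 5%, b = 1 − 0.95^0.125 = 0.64%. For p_sham = 20%, b = 1 − 0.80^0.125 = 2.75%.

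| True sham / active | b | Observed sham / active | Risk ratio | Risk difference (points) |
|---|---|---|---|---|
| 5% / 20% | 0 | 5.0% / 20.0% | 4.00 | 15.0 |
| | 0.64% | 5.6% / 20.5% | 3.66 | 14.9 |
| | 3% | 7.85% / 22.4% | 2.85 | 14.55 |
| | 5% | 9.75% / 24.0% | 2.46 | 14.25 |
| 20% / 40% | 0 | 20% / 40% | 2.00 | 20.0 |
| | 2.75% | 22.2% / 41.7% | 1.88 | 19.45 |
| | 5% | 24% / 43% | 1.79 | 19.0 |
| | 10% | 28% / 46% | 1.64 | 18.0 |
| | 15% | 32% / 49% | 1.53 | 17.0 |

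The larger shifts need a gap week much worse than an ordinary week. With a 5% sham rate over 56 days, 5% in 7 days is an eightfold onset rate, and 3% is ln(0.97)/[0.125 × ln(0.95)] = 4.75-fold.

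**Step 4: after the fix.** With a checklist reading at the second baseline visit, the window before device issue falls from up to 7 days to 0.

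**The case against.** The case for leaving the plan alone is reasonable, and much of it stands.

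- **No counting rule is given.** A reader might infer that gap symptoms are counted as treatment-emergent. The documents do not say so: the stated aim is events that emerge or worsen during treatment, and the open-ended question, the log booklet or the physician's assessment could each establish an earlier onset. This limits the point to possible misclassification. It does not remove it, because none of these tools is said to record onset dates or to cover the gap.
- **Intake distress.** A reader might infer that the plan expects its interviews to make subjects worse. It raises this only as a possibility: "some subjects may suffer a worsening of symptoms as a result of the assessments or discussing traumatic experiences during the intake process". That paragraph adds that no significant change is foreseen, and the risk-management text anticipates any worsening to be brief and mild. PTSD and depressive worsening would also be caught by the three repeated scales. Ordinary symptom fluctuation is enough to support the point.
- **Order of assessments.** Nothing shows that the enrollment checklist precedes the trauma interviews. Table 1 places them in the same Week 0 column without an order.
- **Direction.** A stale reference can also hide events. A symptom present at enrollment that resolves in the gap and recurs on treatment would not look new. This partly offsets the inflation by an unknown amount.
- **Importance.** The gap is short, allocation is blinded and 1:1 with 37 per arm, no formal test of adverse events is described, and the study is called preliminary. All of this is correct and sets the severity.

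**Conclusion.** The point holds as a minor one. The text expressly leaves the SAFTEE-SI out of the second baseline visit, so symptoms that begin or worsen in a window of up to 7 days before device issue may be misclassified as treatment-emergent. The likely result is modestly higher absolute rates in both arms alike in expectation and slight dilution of the risk ratio. The risk difference hardly moves at coherent background rates, no arm is favored, and the efficacy endpoint is unaffected.

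The size cannot be derived from the documents. The figures above assume event rates, a constant background, persistence of gap symptoms and counting against enrollment. A reader might multiply 55 items by 74 subjects (4,070 item comparisons) by some percentage to obtain a count of false events. The documents supply no such percentage, so a count of that kind should not be reported as a finding.

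**What to change.** In section 13, Conduct of the study, add the SAFTEE-SI and its open-ended question to the measures repeated at the second baseline visit, to be completed before the stimulator is handed over. Give that visit its own column in Table 1. Where the SAFTEE-SI is described, define treatment-emergent as new or worse relative to that reading. Changes between enrollment and the second baseline visit can then be reported separately as arising before the device.

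The cost is one extra 55-item self-report per subject at a visit that already takes place. A weaker alternative is to define treatment-emergent as onset or worsening after first device use and to record onset dates. That adds no form but relies on recall. With neither in place, the gap cannot be reliably separated afterwards.
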